9.1.6 Vital Signs

Vital signs will include body temperature (*aural*), supine blood pressure (after 5 minutes resting), respiration rate and pulse rate (after 5 minutes resting). Vital signs will be measured daily during the in-house period.

On clamp days, vital signs will be assessed pre-clamp and post-clamp procedures.

Vital sign measurements will be performed at days indicated in the [Schedule of Events \(SOE\)](#). Additional measures will be performed as deemed necessary by the Principal Investigator.

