9.1.11 ECG Procedure

A standard 12-lead ECG will be recorded after 5 minutes in a supine position.

The Principal Investigator (or designee) will interpret the ECG's by use of an electronic measurement using the following categories: within normal limits, abnormal but not clinically significant, or abnormal with clinical significance. ECGs are performed according to the [Schedule of Events \(SOE\)](#). The following parameters will be recorded

from the subject's ECG trace as calculated by the machine algorithm: heart rate, QT interval, PR interval, QRS interval, RR interval, and QTc (corrected) using the Fridericia correction ($QTcF = QT \div \text{cube root of the R-R interval}$ [where R-R is the duration of the entire cardiac cycle]).

When ECGs are to be collected at the same time point as a blood collection, ECGs should be collected first to avoid any artificially increased heart rates due to the blood collection.

ECGs on clamp days will be performed before and after the clamp procedure.

In some cases, it may be appropriate to repeat abnormal ECGs. If a machine-read QTc value is prolonged, repeat measurements may not be necessary if the Principal Investigator's interpretation determines that the QTc value is in the acceptable range.

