9.1.24 Hepatic Ultrasound Insonification

Patients should report if they need/participate in any outside ultrasound procedures during study.

All three insonifications will be performed after an overnight fast (no food or drinks except for water for at least 10 hours) at approximately the same time on each day. Insonification will start at approximately 07:00 h each day. If multiple subjects are scheduled for insonification on one day, insonification may be staggered and performed between 07:00 h and 08:30 h on that day. Clock time of insonification will be recorded and the same subjects (intra-individual) will undergo their insonification at approximately the same time (actual time) on each day. A window of \pm 15 minutes will be allowed.

Insonifications will be performed prior to any other assessment, such as OGTT or start of H-E clamp.

Check of Imaging Criteria on Day 15:

If sonographer is not able to visualize or stimulate target area on ultrasound, or a measured distance from the skin surface to the porta hepatis target exceeds 10 cm, subjects will be excluded from the study and may be replaced.

For details on the hepatic ultrasound insonification, image saving, data recording and data transfer, please see the Operations Manual and the customized instructions on pulsed insonification in the elastography setting.

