Study Intervention/ Insonification						X	X	X			
Informed consent	X										
Assess eligibility criteria	X										
Re-assess eligibility criteria		X**									
Demography	X										
Medical history	X										
Sequestered in clinic/unit		X	X	X		X	X	X	X		
Physical examination (PE)	X										
Abbreviated PE		X				X			X		X
Hematology, serum chemistry & urinalysis	X	X				X			X		X
Coagulation	X										
TSH	X										
HbA1c	X	X				X			X		X
Hep B, Hep C, HIV	X										
Pregnancy test (urine)		X			X	X				X	X
Pregnancy test (serum)	X										
FSH if postmenopausal	X										
Urine drug screen & alcohol breath test	X	X			X	X				X	X
Weight, BMI	X	X	X		X	X		X		X	X
Height	X										
Waist circumference	X										
Hepatic ultrasound (Screening only)	X										
Vital signs	X	X	X	X	X	X	X	X	X	X	X
12-lead ECG	X	X		X		X		X			X

ASSESSMENTS	SCREENING PERIOD	IN-HOUSE PERIOD 1		OPV	IN-HOUSE PERIOD 2			OPV	F/U		
		Observational Period 1 (Days -1 to Day 14)			Insonification (Days 15-17)						
Visit/ Timepoint (Day)	Start Day—50	-1	1	2	8	15	16	17	18	22	28
Study Intervention/ Insonification						X	X	X			
Instructions on SMBG /glucose via fingerstick to measure during outpatient periods (Days 3-14 and 19-27)		X									
Record concomitant medications	X	X	X	X	X	X	X	X	X	X	X
Record ADEs	X	X	X	X	X	X	X	X	X	X	X
Standardized meals		X	X	X		X	X	X	X		
CGMS		X	X	X	X	X	X	X	X	X	X
CGMS sensor insertion/ change		X			X				X		
Overnight fast ≥ 10 hours			X	X	X	X	X	X	X	X	X
Check of imaging criteria						X					
OGTT			X				X				
Insulin and glucose tracer infusion overnight			X	X			X	X			
Blood sampling for EGP				X				X			
Initiation of Clamp procedure				X				X			
Fasting plasma glucose			X	X	X	X	X	X	X	X	X
HOMA-IR			X			X			X		X
Exploratory biomarkers for assessment and potential storage			X			X			X		X
Glucose parameters (e.g., Fructosamine)			X			X			X		X
Lipid metabolism parameters (e.g. FFA, triglycerides)			X			X			X		X
Inflammatory biomarkers (e.g., adiponectin, CRP)			X			X			X		X

*Study Visit to be performed \geq 30 days after hepatic ultrasound screening examination.

**Necessary laboratory analyses and examinations need to be performed prior to Day -1, so that all eligibility criteria from screening can be re-assessed on Day -1. Re-assessment can be performed after a 30-day wait period, starting after the ultrasound examination.

Table 16-3 Toronto Clinical Neuropathy Scoring System

Toronto Clinical Neuropathy Scoring System		

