2.2. Secondary Objectives and Endpoints

To evaluate safety and tolerability of hepatic ultrasound insonification in subjects with T2DM, assessed by:

- Incidence and severity of adverse device effects (ADEs) [including, liver injury]
- Incidence and severity of clinically significant laboratory abnormalities
- Change from baseline in vital signs (blood pressure, temperature, respiratory rate, and heart rate)
- Incidence and severity of clinical findings on physical examination
- Change from baseline in 12-lead electrocardiogram (ECG) parameters; the primary ECG endpoint will be QTcF

To evaluate the effect of hepatic ultrasound insonification on changes from baseline in whole-body insulin sensitivity during a two-step hyperinsulinemic, euglycemic clamp (HE Clamp), assessed by:

- Insulin Sensitivity Index (SI)

- Glucose disposal rate during steady state (M)
- Glucose metabolic clearance rate during steady state (MCR)

To evaluate the effect of hepatic ultrasound insonification on change from baseline in glucose tolerance and insulin secretion, assessed by an oral glucose tolerance test (OGTT)

- Area under the curve (AUC), total and incremental time, e.g., $AUC_{0-180\text{min}}$

To evaluate the effect of hepatic ultrasound insonification on glucose metabolism parameters, assessed by:

- Change from baseline in blood glucose (BG) profiles assessed with continuous glucose monitoring system (CGMS)
 - Time spent in defined glucose ranges
 - Average daily glucose
 - BG variability parameters (e.g., coefficient of variation as percentage of mean level [% CV], etc.)
 - Low blood glucose index (LBGI)
 - High blood glucose index (HBGI)
- Change from baseline in Homeostasis Model Assessment of Insulin Resistance (HOMA-IR)
- Change from baseline in Homeostatic Model Assessment of Insulin Secretion (HOMA-B)
- Change from baseline in fasting plasma glucose (FPG)

2.3.Exploratory/Other Objectives and Endpoints

To evaluate the effect of hepatic ultrasound insonification on glucose/metabolism parameters, assessed by:

- Change from baseline in exploratory biomarkers (blood samples will be stored for potential later analysis), e.g., but not limited to:
 - Glucagon
 - Glucagon-like peptide 1 (GLP-1), total
 - Leptin
 - Ghrelin
- Change from baseline in long-term glucose parameters
 - Hemoglobin A1c (HbA1c)
 - Fructosamine
- Change from baseline in lipid metabolism parameters
 - Free fatty acids (FFAs)
 - Triglycerides (TG)
 - Total cholesterol

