5.4. Baseline, Post-Baseline Changes, and Last Observed Value (LOV)

Unless stated otherwise, baseline and post-baseline change values will be based on the following:

Baseline will be based on the last non-missing value collected prior to the first on study HUI. Post-baseline values will be those collected after initiation of the first HUI.

Change from baseline is defined as: value – baseline value.

Percent change from baseline is defined as: $[(\text{value} - \text{baseline value})/\text{baseline value}] \times 100\%$.

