The number and percent of subjects of subjects with a clinically significant laboratory abnormality will be summarized by laboratory parameter and study visit. In addition, a summary of laboratory toxicity grades will be prepared by laboratory parameter and study visit.

The denominator for percentages will be the number of subjects with data for the given parameter and visit.

Clinical chemistry and hematology parameters will be reported based on the International System of Units (SI). Observed values and changes from baseline for laboratory evaluations will be summarized at each visit post initiation of HUI. Baseline is defined as the last non-missing value collected prior to first hepatic ultrasound insonification.

A listing of laboratory abnormalities will be provided as will a listing of all laboratory parameters.

Vital signs

Sponsor: GE Research
Protocol Number: GE-HUI-01
Version and Date: Final v2.0, 30JUN2021

Absolute values and changes from baseline will be summarized for vital signs parameters at specified timepoints in the protocol Schedule of Events.

Vital signs include: systolic and diastolic blood pressure (mmHg), temperature (C), respiratory rate (bpm), and heart rate (bpm). Observed values and changes from baseline for vital signs will be summarized at each visit and time point.

All vital signs data will be listed.

Physical examination

A summary of physical examination (PE) findings will be presented by body system as recorded on the eCRF. The number of subjects and percent will be summarized based on abnormal examination results (abnormal without clinical significance and abnormal with clinical significance) by visit. The number and percent of subjects with any abnormal finding will also be provided. The denominator will be the number of subjects with a physical examination performed at the visit.

Physical examination findings will be listed by subject.

Electrocardiogram (ECG)

Absolute values and changes from baseline will be summarized for 12-lead ECG parameters at specified timepoints. The primary ECG endpoint will be QTcF.

ECG parameters include: QT interval (ms), PR interval (ms), QRS interval (ms), RR interval (ms), QTcF (ms). Observed values and changes from baseline for ECG data will be summarized at each visit and time point.

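### Day 17 QTcF is compared with a baseline taken without insulin, and no paired change against the time-matched Day 2 clamp-day ECGs is planned

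*SAP*

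**What the plan says.** QTcF is named within the secondary safety objective (SAP 2.2): "Change from baseline in 12-lead electrocardiogram (ECG) parameters; the primary ECG endpoint will be QTcF". The general baseline rule in SAP 5.4 is: "Baseline will be based on the last non-missing value collected prior to the first on study HUI". It applies unless stated otherwise, and SAP 6.9 states no exception for ECG or vital signs. For ECG, SAP 6.9 plans: "Observed values and changes from baseline for ECG data will be summarized at each visit and time point". For vital signs it plans: "Observed values and changes from baseline for vital signs will be summarized at each visit and time point".

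The readings come from the protocol. Section 9.1.11: "ECGs on clamp days will be performed before and after the clamp procedure". Section 9.1.6: "On clamp days, vital signs will be assessed pre-clamp and post-clamp procedures". The clamp days are Day 2, before any insonification, and Day 17, the day of the third insonification.

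For the clamp parameters M, MCR and M/I, SAP 6.7 names the Day 2 values as baseline for the corresponding Day 17 values. SAP 6.9 likewise pairs similar in-house periods for CGMS: Day -1 to Day 1 against Day 15 to Day 16.

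**The concern.** A change from baseline isolates the device only if the two readings differ in nothing else that matters. The Day 15 reading is taken at a fasting morning check-in. The Day 17 pre-clamp reading follows an overnight IV insulin infusion started at about 22:00. The Day 17 post-clamp reading follows that infusion and a 6-hour clamp whose second step runs at 120 mU/m²/min for 180 minutes, which protocol 9.1.22 describes as supraphysiological.

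There is no control arm. If insulin or the clamp moves QTcF, heart rate or blood pressure, the Day 17 change could look like a device signal, or could hide one. The readings that would remove the shared part are already scheduled on Day 2, but no change is derived from them.

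**Working it through.** No figure in the plan needs reproducing: the sample size of 15 was set empirically, and no QTcF effect or variance is given. The check traces the baseline rule through the schedule.

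**1. Which ECGs exist.** Table 16-1 carries six marks ("12-lead ECG X X X X X X"). In Table 16-2 they fall at Screening and Days -1, 2, 15, 17 and 28. Protocol 6.2 also lists ECGs at the Day 8 and Day 22 outpatient visits, which the Schedule of Events omits. On either reading, Day 17 is the only ECG day after Day 15 and before the later non-clamp visits (Day 22 or Day 28).

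**2. What each contrast contains.** Let B be a subject's QTcF with no insulin running and D the insonification effect by Day 17. Let O be the overnight-insulin effect at the pre-clamp reading, and C the total overnight-insulin and clamp effect at the post-clamp reading. Subscripts 2 and 17 give the day.

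- Day 15 = B
- Day 2 pre = B + O₂; Day 2 post = B + C₂
- Day 17 pre = B + D + O₁₇; Day 17 post = B + D + C₁₇

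| Contrast | Pre-clamp | Post-clamp |
|---|---|---|
| Planned: Day 17 − Day 15 | D + O₁₇ | D + C₁₇ |
| Matched: Day 17 − Day 2 | D + (O₁₇ − O₂) | D + (C₁₇ − C₂) |

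The planned contrast carries the whole insulin or clamp effect. The matched contrast carries only the difference between the two clamp days. Protocol 9.1.22 plans the same Step 1 and Step 2 rates and the same schedule on both days, so a common effect cancels.

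**3. Size under assumptions.** C, O and the within-subject SD s are assumed, because the documents give none. With n = 15, D = 0 and independent readings of equal SD, the 95% CI half-width for a paired change is t(0.975; 14) × s√2 / √15 = 2.145 × s × 1.414 / 3.873. That is 3.9, 6.3 or 7.8 ms for s = 5, 8 or 10 ms. It is the same for both contrasts, so under these assumptions matching costs no precision.

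A simulation of 20,000 trials with s = 8 ms and equal effects on both clamp days gave:

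| Assumed effect | Mean of planned change | 95% CI excludes 0, planned | 95% CI excludes 0, matched |
|---|---|---|---|
| C = 0 ms (post) | 0 ms | about 5% | about 5% |
| C = 5 ms (post) | 5 ms | 36% | about 5% |
| C = 10 ms (post) | 10 ms | 89% | about 5% |
| C = 15 ms (post) | 15 ms | 99.8% | about 5% |
| C = 20 ms (post) | 20 ms | 100% | about 5% |
| O = 2 ms (pre) | 2 ms | 10% | about 5% |
| O = 5 ms (pre) | 5 ms | 36% | about 5% |

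The SAP plans no test of QTcF; the CI columns only show how large the mixed-in effect would be against sampling noise.

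**4. Vital signs.** The Schedule of Events has vital signs at every visit. Those on Days 16, 18 and 22 are not clamp-day readings and are compared with a non-clamp baseline. Day 18 is the day after the last insonification. The algebra above applies to Day 17 vital signs, but other near-treatment vital signs exist.

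**5. Order on Day 15.** Protocol 9.1.24 says: "Insonifications will be performed prior to any other assessment, such as OGTT or start of H-E clamp". The examples it gives are the OGTT and the clamp. Section 6.2 has the Day 15 fasting bloods drawn before any assessment, section 9.1.8 places safety sampling before planned procedures, and section 9.1.11 puts an ECG ahead of a blood draw at the same time point. Together these suggest, without stating it, that the Day 15 ECG comes first. If it did not, the baseline would fall back to Day 2 post-clamp under the Schedule of Events, or to Day 8 under section 6.2. The Day 2 fallback would match Day 17 post-clamp, but would put −C₂ into the Day 28 change.

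**The case against.** The strongest reply is that the tables already allow the comparison. SAP 6.9 limits laboratory summaries to visits after insonification starts but sets no such limit for ECG or vital signs. Day 2 pre- and post-clamp observed values should therefore sit in the same tables as Day 17, and all values are listed by subject. With complete data, the mean matched change is the difference of two printed means. This stands, so it would be wrong to infer that nothing in the tables separates clamp from device. What is missing is the paired change and its spread: its variance is s₁₇² + s₂² − 2r·s₁₇·s₂, and the correlation r is not printed. The difference of means also fails if a subject has Day 2 but not Day 17 data.

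A reader might infer that the plan will report a clamp effect as an insonification effect. The documents do not support that. They establish no clamp effect on QTcF, and the SAP tabulates by visit and time point without attributing the change. Pre- and post-clamp rows are also kept separate, so the clamp itself enters only the post-clamp row.

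A reader might also infer that the Day 2 contrast equals the device effect and should replace the planned one. It need not: overnight insulin is titrated to glucose (protocol 9.1.20), infusion rates may be adjusted at the investigator's discretion (9.1.22), and the two clamps are about two weeks apart.

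Finally, this is a descriptive secondary summary in an exploratory pilot, with no QTcF margin or decision rule. That limits the weight of the point but does not remove it.

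**Conclusion.** The point holds, chiefly for ECG. As planned, the Day 17 QTcF change cannot by itself distinguish insonification from overnight insulin (pre-clamp row) or from overnight insulin plus clamp (post-clamp row). The same applies to Day 17 vital signs, with less consequence because of the non-clamp readings on Days 16, 18 and 22.

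The mixing is one for one, but its size is unknown: every millisecond figure above is an assumption, and if the clamp effect is zero both contrasts agree. The conclusion assumes that the Day 15 ECG precedes insonification and so serves as baseline; the documents suggest this but do not state it. A post-clamp Day 2 baseline is a possibility to close off, not something the plan prescribes.

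**What to change.** In SAP 6.9, for ECG (QTcF first) and Day 17 vital signs, add the within-subject change from Day 2 at the same time point: pre-clamp with pre-clamp, post-clamp with post-clamp. Use it when interpreting Day 17 for a device effect. Keep the planned change from baseline beside it, and note that matching removes only the clamp effect common to both days.

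Also:

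- state in SAP 5.4 or 6.9 that post-clamp readings do not serve as baseline for non-clamp visits;
- confirm in the protocol that the Day 15 ECG and vital signs precede the first insonification;
- reconcile protocol 6.2, which lists ECGs on Days 8 and 22, with the Schedule of Events.

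The cost is one more summary per parameter and a few clarifying sentences. The matched change uses only readings already scheduled.
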